Substudy 1 is an evaluator blinded randomized controlled trial with follow-up after 3, 6, 9 and 12 months. Patients not satisfied with the outcome in substudy 1 after at least 1 month of training, have the possibility to drop-out of this substudy and be included in substudy 2. Drop-outs are recorded as “non-survivors” and a "Survival" curve is recorded for each exercise group. A total of 90 patients are included, 45 patients in each of the 2 training groups. All patients will be included in the intention to treat analysis, but we will also perform a per-protocol analysis only including patients performing at least 75% of the training programs.

Anyone who ceases due to unsatisfactory effect in sub-study 1 can be included in the second part of the study after at least 1 months of training and no later than after 12 months.

Sub-study 2

Single blinded (assessor and statistics) Randomized Controlled Trial.

Randomization method

Randomization must be preceded by informed consent and power of attorney. The randomization of patients is performed by an independent office employee not involved in patient care ([name]) using a computer generated randomization schedule (MINIMPY, Maghaei 2010) using permuted block sizes (two to four). The employee is blinded to the block sizes. The allocation of each patient is stored in a computer drive with exclusive access only for the responsible office employee ([name]). Patients will be divided equally into 4 groups. No further stratification will be carried out in part 2 of the study.

The secretary is then in charge of filling out randomization sheets and preparing the CRF (clinical research files).

Blinding

The study will be evaluated blinded. The doctors who give the injections cannot be blinded due to the large difference in the injection volume. Patients cannot be blinded to the training performed and can probably feel whether a small or large volume is being injected. The effect of the training is evaluated monthly by the patient himself at home without interference with any investigators on an app (Redcap). At every doctors appointment US assessment of the Achilles tendon will be performed.

The 4 secondary treatment arms

Patients continue in the allocated training (Heavy Slow Resistance exercise or App guided training) and treatment is supplemented with either corticosteroid injection (CS) or High Volume Injection (HVI). This results in 4 groups:

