Substudy 2 is also an evaluator blinded randomized controlled trial with follow up after 1,2,3,6,9,12 months.

Anyone who ceases due to unsatisfactory effect in sub-study 2 can be included in the third part of the study after at least 3 months of exercise therapy and no later than after 12 months.

Sub-study 3:

Open prospective study

Patients who do not achieve sufficient efficacy from conservative treatment in sub-studies 1 and 2 will be offered surgery with tenolysis, which is the standard treatment for patients with Achilles tendonopathy who do not respond adequately to conservative treatment. The operation is performed at the Sports Surgery Section, Orthopaedic Surgery Department, Bispebjerg Hospital.

Description of the operation

The patient is operated on in lower leg block or universal anesthesia.

Preoperative antibiotics with either Dicillin 2 g iv or Zinacef 11/2 g iv.

The thickening of the tendon is determined by palpation. Incision (about 3 cm long) is made corresponding to the anterior/medial edge of the tendon along the thickened part of the tendon. The peritendium is cleaved and the tendon is released from the peritendium throughout the circumference corresponding to the swelling and approximately 3 cm distally and proximally to the swelling. Afterwards the skin is closed with nylon sutures.

Trial Design

Open prospective quality assurance study with follow-up 3, 6 and 12 months after surgery

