4 OUTCOME MEASURES

Primary outcome measures:

The primary endpoints in sub-study 1: VISA-A at 3 and 6 months. Collected by independent evaluator via “Redcap”.

The primary endpoints in sub-study 2: VISA-A (total and pain subscales) 6 months after the 1st injection date in substudy 2. Collected by independent evaluator via “Redcap”.

The primary endpoints in sub-study 3: VISA-A score at 6 and 12 months from the day of surgery.

All patients are thoroughly instructed in visa-A score, on all visits, as it can be difficult to understand. However, it is important that they fill out the score at home directly in the assessment-

app: "Redcap" without interference of any involved investigators. Intention to treat is used so that patients who do not show up for primary outcome will have scores transferred from the last attendance.

Secondary outcome measures

Sub-study 1:

Lickert scale at 3, 6, 9 and 12 months: 11 point box scale from -5 to +5, where 0 is the status at **entry**, +5 is cured, and -5 is much worse.

VISA-A scores 1,2, 9 and 12 months, including VISA-A pain subscore during Function at all timepoints (1,2,3,6,9,12 months)

Assessment of the exercise therapy at 3 months: 11 point box scale from 0-10, where 0 is very uninspiring / boring training, and 10 is very inspiring and motivating training.

Thickness of the Achilles tendon measured by ultrasound scan, cross-sectionel image on the thickest of the tendon at 3, 6, 9 and 12 months. The thickness of the "healthy" tendon is also measured for comparison.

Ultrasound Scanning Doppler Activity assessed with Color Doppler at 3, 6, 9 and 12 months.

After 6, 9 and 12 months, it is also assessed how many percentage of previous activity level (from before the injury) they have recovered. The patient himself states this as a percentage.

Survival rate to the treatment is assessed by assessing all patients that are not satisfied with the treatment or can not comply to the training protocol.

Sub-study 2:

VISA-A score 1, 2, 3, 9 and 12 months

Thickness of the Achilles tendon measured by ultrasound scan, cross-sectional image on the thickest part of the tendon at 3,6,9,12 months. The thickness of the "healthy" tendon is also measured for comparison.

Ultrasound Scanning Doppler Activity assessed with Color Doppler at 3, 6, 9 and 12 months.

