5 SAMPLE SIZE AND POWER

Sub-study 1

The risk of finding a difference between groups, even if there really is none, is set at 5% (risk of type I error), while the risk of overlooking a difference between the groups that is actually present is set at 20% (type II error). All outcome parameters will be analyzed using Mixed Effect Analysis

Statistical Analysis Plan	Date: nov 27, 2022
Exercise/Injections/operation in Achilles midsubstance tendinopathy	
Bispebjerg Hospital	

with treatment regime (group) and time as main factor (GraphPad Prism version 9.3 for Windows, GraphPad Software, La Jolla California USA, www.graphpad.com). All analysis are performed as an intention-to-treat analysis. If a patient drops out due to no improvement or too much pain to continue exercise therapy, the missing data will still be included using the mixed effect analysis.

Q-Q plots will be visually examined prior to analysis to ensure that the assumption of normal distribution is not violated. Significance level is set to 0.05. We will also compare the “survival rate” in each training group, and compare the end result after training by performing per protocol analysis. Patients not complying at least 75% with the training protocol are not included in the per-protocol statistics.

The minimum relevant difference in VISA-A is set at 15. However, as a non-inferiority study, the difference is set to $15/2 = 7.5$. Based on other studies on pain intensity, we expect a mean baseline of 50 and an average improvement of 17. The standard deviation (SD) on the VISA-A measurements in these studies is 13. Power of 80% gives a sample size of 38 participants in each group. We plan to include 45 in each group in case of data loss and no-shows, for a total of 90 patients.

Sub-study 2:

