In a previous study, 25% achieved satisfactory effect from training alone. If the same is seen in the current study, approximately 67 will want additional treatment. Of these, we expect that 50 will continue in sub-study 2. Sub-study 2 is a superiority study, and 22 patients are needed to have an 80% chance of finding, with 5% significance level, a difference in VISA-A scores of more than 11 between treatment groups using Mixed Effect Analysis using the intention to treat principle. Patients are divided into 4 groups, but this sub study will be powered to detect differences between exercise therapy+HVI and Exercise therapy +CS injection. This means that the combination of group 3 and group 5 are compared to the combination of group 4 and group 6. However, we will also compare group 3 to group 4, and group 5 to group 6.

Q-Q plots will be visually examined to ensure that the assumption of normal distribution is not violated prior to analysis.

Sub-study 3

	Statistical Analysis Plan	Date: nov 27, 2022
Bispebjerg Hospital	Exercise/Injections/operation in Achilles midsubstance tendinopathy	

is a prospective quality assurance study. Paired T-test is used for calculating differences from before operation to 3, 6 and 12 months after operation. Change in VISA-A score is the primary outcome at 6 and 12 months, with an expected preoperative score of 50 and a relevant improvement is set to 15. The standard deviation of the difference is from earlier studies 13. In order to record an improvement of at least 15 points with a risk of type I error of 5% and type II error of 20%, 8 patients would have to be included in this study.

Data processing:

Entry data is registered in Redcap, where all information from each individual subject is collected.

Each patient is assigned an anonymous unidentifiable project number: Ach2019-n.

Project numbers are listed on all CRF and patient diaries.

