7 STATISTICAL ANALYSES

7.1 General

In substudy 1 and 2 we will perform a Mixed Effect Analysis. Intention to treat is used so that patients who do not show up for primary outcome will still be included.

In substudy 3 we will perform a paired t-test.

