7.2 Statistical Analysis Plan

Statistical analysis will be undertaken using PRISM version 9.3.1. All analyses will be conducted on an intention-to-treat principle using all randomized participants in the groups they were originally randomized to. A blinded statistician will perform the data analysis. In the per-protocol analysis only patients complying at least 75% with the treatment protocol are included in the statistics.

A blinded statistician will perform the data analysis.

Demographic and anthropometric characteristics (gender, age, mass, height, body mass index, sporting activities and pain duration) will be determined at the baseline visit for each treatment group.

Statistical analyses will be conducted on all outcome measures at all timepoints. However, the primary end-point will be the total score of the VISA-A questionnaire at 3 and 6 months in substudy 1; VISA-A total score and pain-subscales at 6 months in substudy 2; and VISA-A total score at 6 and 12 months in substudy 3. Between-group comparisons of treatment effect for all primary and secondary outcomes, will be performed with a mixed effect analysis. To assess for inferiority and superiority, mean between-group differences and two-sided 95% confidence intervals will be calculated.

The ordinal scaled data of patients overall assessment of the treatment effect (Lickert score -5 to +5) will be analyzed with the same mixed effect analysis, if the data is found normally distributed.

The ordinal scaled data on satisfaction with the exercise program is analyzed with the same mixed effect analysis, if the data is found normally distributed.

The ordinal scaled data of grading the flow within the tendon into 4 categories will be calculated using non parametric statistics: Mann-Whitney U-tests.

Return to sport in percent of earlier sports activity will be compared using unpaired t-test if the data is normally distributed, otherwise non parametric analysis (Mann-Whitney) is performed.

In substudy 1 the survival rate in each exercise group is illustrated on a Kaplan-Meier plot and differences are calculated using Log rank test (Mantel-Cox test).

A two-sided P value of less than 0.05 will be considered to indicate statistical significance.

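### Two unreconciled rules for no-shows at the primary visits in sub-studies 1 and 2: last score carried forward, or mixed effect analysis on observed scores

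*SAP*

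**What the plan says.** Section 4, at the end of the primary outcome measures, gives a rule under the name of intention to treat: "patients who do not show up for primary outcome will have scores transferred from the last attendance". It follows the endpoints of all three sub-studies.

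The other places point to a model:

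- Section 5, Sub-study 1, plans a mixed effect analysis for all outcomes. If a patient "drops out due to no improvement or too much pain to continue exercise therapy, the missing data will still be included" through that analysis.
- Section 5, Sub-study 2, is powered for a difference "between treatment groups using Mixed Effect Analysis using the intention to treat principle".
- Section 7.1 prescribes the mixed effect analysis for sub-studies 1 and 2. It then uses the opening words of Section 4 again with a different ending: "patients who do not show up for primary outcome will still be included".
- Section 7.2: "Between-group comparisons of treatment effect for all primary and secondary outcomes, will be performed with a mixed effect analysis". It also analyses by intention to treat, "using all randomized participants in the groups they were originally randomized to".

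On patients who change sub-study, Section 3 says that those dissatisfied after at least one month of training "have the possibility to drop-out of this substudy and be included in substudy 2". It records them as drop-outs and keeps all patients in the intention-to-treat analysis.

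**The concern.** Carry-forward and a mixed model on observed scores are two different ways of handling a missing VISA-A. The first sets the missing value equal to the last one seen. The second estimates the visit mean from the observed scores and their correlation over time. They generally give different estimates and standard errors. A third procedure, filling first and then fitting the model, would also fit the words of the SAP.

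The SAP ranks none of these and calls none a sensitivity analysis. For sub-study 1 the result is a confidence interval set against a 7.5-point non-inferiority margin, so a shift of a fraction of a point can decide a close case. The blinded statistician and coded groups (Sections 5 and 7.2) guard against a choice that knowingly favours one arm. They do not fix the rule in advance.

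**Working it through.** **Side by side**

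| Place | Patients | Rule |
|---|---|---|
| Section 4 | no-shows at the primary outcome | last score carried forward |
| Section 5, Sub-study 1 | drop-outs for no improvement or pain | mixed effect analysis |
| Section 5, Sub-study 2 | intention-to-treat comparison | mixed effect analysis; missing scores not mentioned |
| Section 7.1 | no-shows at the primary outcome, sub-studies 1 and 2 | included; carry-forward not mentioned |
| Section 7.2 | all randomised, all between-group comparisons | mixed effect analysis |

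The first and fourth rows concern the same patients. No text reconciles them.

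**The plan's own figure.** With margin 7.5, SD 13, power 80% and one-sided 5%, n = 2 × 13² × (1.645 + 0.842)² / 7.5² = 37.2, so 38 per group as stated. The missing-data rule does not enter this figure, and the point does not dispute it.

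**What carry-forward does to the sub-study 1 difference.**

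From the SAP: 45 per arm, mean gain 17, margin 7.5. Seven leavers per arm is the plan's own allowance (45 - 38).

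Assumed, because the SAP gives no timing: HSR gains 17 and the app 9.5 (true difference -7.5, app minus HSR); the last visit is equally likely at month 1, 2 or 3; leaving is unrelated to the score; gain is linear, over 6 months or over 3.

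Let h and a be the leavers in the HSR and app arms, and s the mean share of the final gain reached at the last visit. The expected month-6 difference after carry-forward is

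D = -7.5 + (1 - s)(17h - 9.5a)/45.

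- Build over 6 months: s = (1/6 + 2/6 + 3/6)/3 = 1/3.
- Build over 3 months: s = (1/3 + 2/3 + 1)/3 = 2/3.

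| HSR / app leavers | 17h - 9.5a | D, 6-month build | D, 3-month build |
|---|---|---|---|
| 7 / 7 | 52.5 | -7.5 + 0.78 = -6.72 | -7.5 + 0.39 = -7.11 |
| 6 / 8 | 26 | -7.5 + 0.39 = -7.11 | -7.5 + 0.19 = -7.31 |
| 5 / 9 | -0.5 | -7.5 - 0.01 = -7.51 | -7.5 - 0.00 = -7.50 |
| 4 / 10 | -27 | -7.5 - 0.40 = -7.90 | -7.5 - 0.20 = -7.70 |

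The bias vanishes when 17h = 9.5a, that is, when the app loses 17/9.5 = 1.79 times as many patients as HSR. Below that ratio a true deficit shrinks; above it the deficit grows. With the 3-month build, the same figures hold at month 3.

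If the arms are truly equal (both gain 17), D = (1 - s) × 17 × (h - a)/45. With 5 and 9 leavers and s = 1/3 this is (2/3) × 17 × (-4)/45 = -1.0, a spurious deficit for the app.

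**Does the choice change verdicts?** Simulation, 4,000 runs per case: SD 13, correlation 0.5, 7 leavers per arm, those with the poorest month-1 change leaving; random-intercept model with arm-by-visit means; month-6 two-sided 95% interval against 7.5. Paired figures are for the 6-month / 3-month build.

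- True difference -7.5: filled and then modelled, false non-inferiority is 4.2% / 3.3%. Modelled on observed scores, it is 2.0 to 2.8%, with a mean between -7.46 and -7.50. The two procedures disagree in 2.1% / 2.1% of trials.
- True difference -3.75: they disagree in 9.7% / 9.5% of trials.

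The first line depends on equal leaving. With 5 HSR and 9 app leavers (6-month build, carry-forward and a t-test, 6,000 runs), false non-inferiority is 1.7% if the poorest changers leave and 2.2% if leaving is random. With 4 and 10 it is 1.0% and 1.6%.

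Leaving in these runs depends only on observed scores or on chance, the condition that suits the mixed model. No figure was computed for sub-study 2.

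**The case against.** The best defence is that the rules are complementary: Section 4 covers patients who miss a visit, Section 5 covers those who drop out for no improvement or pain, and Section 7.1 only says that no-shows are included, not how. This is a possible reading, but the SAP does not state the split. Section 7.1 places no-shows directly after prescribing the model, and a drop-out also fails to appear at the primary visit. The defence has more force for sub-study 2, where no sentence says outright that the model handles missing scores. There the conflict rests on Section 4 against Sections 5, 7.1 and 7.2.

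Four stronger readings are tempting, and the SAP does not support them.

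- *Carry-forward favours a non-inferiority claim.* This needs roughly equal leaving in both arms. If the app were worse, more app patients might well leave, and the bias would vanish or reverse.
- *Filling scores leaves the model nothing to do.* Section 4 fills only the primary visits. Other visits and outcomes would still have gaps.
- *Scores after a move to sub-study 2 are left open.* Sub-study 2 has "follow up after 1,2,3,6,9,12 months", so a patient who moves at month 1 can have a score under injection at month 3 of sub-study 1. But Section 3 calls movers drop-outs, and Section 5 treats the later data of those who leave for no improvement as missing. The phrase in Section 7.2, "using all randomized participants in the groups they were originally randomized to", says which patients and groups are analysed, not which scores. Only a confirming clause is needed.
- *With 50 of 90 expected to move, carry-forward would distort far more, or the allowance from 38 to 45 is too small.* Section 5 sends drop-outs for no improvement to the model, the timing of moves is not given, and the sample-size figure does not turn on this point.

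**Conclusion.** The contradiction stands and needs no assumption: Section 4 prescribes carry-forward for no-shows at the primary visits, the analysis sections prescribe a mixed effect analysis, and neither is ranked. The primary estimate in sub-studies 1 and 2 is therefore not uniquely defined.

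The numerical effect is modest and its direction is not known in advance. At the plan's own allowance, split equally, the shift is 0.4 to 0.8 points against a 7.5-point margin; modest imbalance removes it, and more reverses it. The sizes rest on the assumed timing, linear gain and, for the simulations, a correlation of 0.5. The chance of opposite verdicts is likewise specific to its scenario: about 2% at a true deficit of 7.5 and just under 10% at 3.75, both with equal leaving. It should be corrected before unblinding, because it concerns the primary result and costs little.

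**What to change.** For sub-studies 1 and 2, delete the carry-forward sentence in Section 4 or label it a sensitivity analysis. State once, in Section 7.2, that the primary analysis is the mixed effect analysis on observed VISA-A scores, with no filling beforehand, and bring Sections 5 and 7.1 into line with it.

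In the same sentence, confirm that VISA-A scores recorded after entry to sub-study 2 are treated as missing in the primary sub-study 1 analysis, as Sections 3 and 5 already imply.

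Sub-study 3 needs no change: its paired t-test does not compete with a mixed model. If the carry-forward sentence is kept for sub-study 3, say that it applies there only.

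Cost: SAP wording and, if carry-forward is kept as a sensitivity analysis, one extra analysis of scores already collected. Visits, treatment and sample size do not change.

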5 SAMPLE SIZE AND POWER

Sub-study 1

The risk of finding a difference between groups, even if there really is none, is set at 5% (risk of type I error), while the risk of overlooking a difference between the groups that is actually present is set at 20% (type II error). All outcome parameters will be analyzed using Mixed Effect Analysis

Statistical Analysis Plan	Date: nov 27, 2022
Exercise/Injections/operation in Achilles midsubstance tendinopathy	
Bispebjerg Hospital	

with treatment regime (group) and time as main factor (GraphPad Prism version 9.3 for Windows, GraphPad Software, La Jolla California USA, www.graphpad.com). All analysis are performed as an intention-to-treat analysis. If a patient drops out due to no improvement or too much pain to continue exercise therapy, the missing data will still be included using the mixed effect analysis.

Q-Q plots will be visually examined prior to analysis to ensure that the assumption of normal distribution is not violated. Significance level is set to 0.05. We will also compare the “survival rate” in each training group, and compare the end result after training by performing per protocol analysis. Patients not complying at least 75% with the training protocol are not included in the per-protocol statistics.

The minimum relevant difference in VISA-A is set at 15. However, as a non-inferiority study, the difference is set to $15/2 = 7.5$. Based on other studies on pain intensity, we expect a mean baseline of 50 and an average improvement of 17. The standard deviation (SD) on the VISA-A measurements in these studies is 13. Power of 80% gives a sample size of 38 participants in each group. We plan to include 45 in each group in case of data loss and no-shows, for a total of 90 patients.

Sub-study 2:

In a previous study, 25% achieved satisfactory effect from training alone. If the same is seen in the current study, approximately 67 will want additional treatment. Of these, we expect that 50 will continue in sub-study 2. Sub-study 2 is a superiority study, and 22 patients are needed to have an 80% chance of finding, with 5% significance level, a difference in VISA-A scores of more than 11 between treatment groups using Mixed Effect Analysis using the intention to treat principle. Patients are divided into 4 groups, but this sub study will be powered to detect differences between exercise therapy+HVI and Exercise therapy +CS injection. This means that the combination of group 3 and group 5 are compared to the combination of group 4 and group 6. However, we will also compare group 3 to group 4, and group 5 to group 6.

Q-Q plots will be visually examined to ensure that the assumption of normal distribution is not violated prior to analysis.

Sub-study 3

	Statistical Analysis Plan	Date: nov 27, 2022
Bispebjerg Hospital	Exercise/Injections/operation in Achilles midsubstance tendinopathy	

is a prospective quality assurance study. Paired T-test is used for calculating differences from before operation to 3, 6 and 12 months after operation. Change in VISA-A score is the primary outcome at 6 and 12 months, with an expected preoperative score of 50 and a relevant improvement is set to 15. The standard deviation of the difference is from earlier studies 13. In order to record an improvement of at least 15 points with a risk of type I error of 5% and type II error of 20%, 8 patients would have to be included in this study.

Data processing:

Entry data is registered in Redcap, where all information from each individual subject is collected.

Each patient is assigned an anonymous unidentifiable project number: Ach2019-n.

Project numbers are listed on all CRF and patient diaries.

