3 STUDY METHODS

Sub-study 1:

Single blinded (assessor and statistics) Randomized Controlled Trial.

Randomization method

Randomization must be preceded by informed consent and power of attorney. The randomization of patients is performed by an independent office employee not involved in patient care ([name]) using a computer generated randomization schedule (MINIMPY, Maghaei 2010) using permuted block sizes (four to six). The employee is blinded to the block sizes. The allocation of each patient is stored in a computer drive with exclusive access only for the responsible office employee ([name]). Patients will be divided equally into 2 groups. Symptom duration will be stratified < 1 year> and VISA-A score (0-100) at entry <50>

The secretary is then in charge of filling out randomization sheets and preparing the CRF (clinical research files).

Blinding

The study will be evaluated blinded. Patients cannot be blinded to the training performed. The effect of the training is evaluated monthly by the patient himself at home without interference with any investigators on an app (Redcap). At every doctors appointment US assessment of the Achilles tendon will be performed.

The 2 primary treatment arms are:

	Statistical Analysis Plan	Date: nov 27, 2022
	Exercise/Injections/operation in Achilles midsubstance tendinopathy	
Bispebjerg Hospital		

GROUP 1 (HSR): Treatment with **Heavy Slow Resistance training** (HSR) thoroughly guided by physiotherapists. The training will take place in a gym and lasts for 3 months. Simultaneous load reduction from harmful activities (running, jumping) is advocated.

GROUP 2 (App): Treatment with 3 months of **home training guided via an app (Injurymap)**. The only aid is a rubber band. Simultaneous load reduction from harmful activities (running, jumping) is advocated.

Description of the load reduction during the controlled training

The first 3 months the patients is advocated to abstain from all jumping and running activities (impact training). They are free to do non-impact training such as cycling, swimming, rowing and strength training. After 3 months of controlled rehabilitation, patients should slowly return to their previous sports activity and level, without provoking further pain or morning stiffness.

Description of Heavy Slow Resistance Exercise

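### Sub-study 1's mixed model names only group and time; leaving out baseline VISA-A and the randomisation strata gives up precision of unknown size

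*SAP*

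**What the plan says.** For sub-study 1, SAP section 5 specifies a mixed effect analysis "with treatment regime (group) and time as main factor". Sections 7.1 and 7.2 repeat the method and name no covariate. Section 7.2 says that for inferiority and superiority "mean between-group differences and two-sided 95% confidence intervals will be calculated", and that "Statistical analyses will be conducted on all outcome measures at all timepoints".

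The randomisation text in section 3 reads: "Symptom duration will be stratified < 1 year> and VISA-A score (0-100) at entry <50>". The schedule in section 7.4 places a VISA-A measurement at allocation. The primary endpoint in section 4 is VISA-A at 3 and 6 months.

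Nowhere does the SAP put baseline VISA-A, symptom duration or the strata into the model. It also does not say whether the baseline score is a level of the time factor.

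**The concern.** The trial takes the trouble to balance two variables that it evidently regards as prognostic, and it measures one of them on the same scale as the primary outcome. The stated model then ignores both. To the extent that entry VISA-A predicts later VISA-A, the interval for the group difference is wider than it needs to be.

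Interval width matters here because non-inferiority is judged by whether the interval excludes a loss of 7.5 points. An app programme that is truly no worse could fail to be shown so, although data already collected would have narrowed the interval. Timing matters too: covariates chosen after unblinding would be a data-dependent choice.

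**Working it through.** **Inputs.** From SAP section 5: margin 7.5, SD 13, power 80%, type I error 5%, 38 needed per group and 45 planned. From section 7.2: two-sided 95% interval. The true difference is taken as 0. The correlation r between baseline and follow-up VISA-A is not given, so it is assumed over the range 0.1 to 0.7.

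**Step 1: the plan's own figure.** n = 2(z₁₋α + z₀.₈)² × 13² / 7.5².

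- One-sided 5%: 2 × (1.645 + 0.842)² × 169 / 56.25 = 37.2, so 38. This reproduces the SAP.
- One-sided 2.5%, which is what a two-sided 95% interval implies: 2 × (1.960 + 0.842)² × 169 / 56.25 = 47.2, so 48.

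The 38 therefore rests on the unadjusted SD and takes no credit for baseline. The gap between 38 and 48 is a separate mismatch in alpha and is not counted here.

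**Step 2: effect of adjustment with complete data.** Adjusting for baseline replaces 13 by 13√(1 − r²). The half-width is t × SD × √(2/38); unadjusted, 1.993 × 13 × 0.2294 = 5.94. Power is from the noncentral t distribution, with one degree of freedom lost for the covariate.

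| r (assumed) | Half-width of 95% CI, 38 per group | Narrowing | Power, one-sided 5% | Power, two-sided 95% CI |
|---|---|---|---|---|
| unadjusted | 5.94 | – | 80% | 70% |
| 0.1 | 5.91 | 0.5% | 80% | 70% |
| 0.2 | 5.82 | 2% | 82% | 72% |
| 0.3 | 5.67 | 5% | 83% | 74% |
| 0.5 | 5.15 | 13% | 89% | 82% |
| 0.7 | 4.24 | 29% | 97% | 94% |

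At one-sided 5%, a gain of 5 power points needs r of about 0.38. With all 45 per group analysed, one-sided 5% power is 86% unadjusted against 88%, 93% and 98% at r = 0.3, 0.5 and 0.7.

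**Step 3: does baseline as a level of time do the same job?** No. I took generalised least squares with equal correlation r over months 0, 1, 2, 3, 6, 9 and 12, complete data and 38 per group. With group-by-time terms, the standard error of the month 3 and month 6 contrasts is 2.98 at every r, the same as 13 × √(2/38). With no group difference allowed at baseline, which is equivalent to covariate adjustment, it is 2.97, 2.92, 2.85, 2.58 and 2.13 for the five values of r. A change-from-baseline contrast does not recover the loss either: its variance factor 2(1 − r) is never below 1 − r².

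**Step 4: what the SD of 13 means.** Section 5 says for sub-study 1 that "The standard deviation (SD) on the VISA-A measurements in these studies is 13", but for sub-study 3 that "The standard deviation of the difference is from earlier studies 13". If 13 is an SD of change, the cross-sectional SD is 13/√(2(1 − r)). Power with the two-sided 95% interval and 38 per group is then 92%, 88%, 84%, 70% and 49% unadjusted, against 92%, 89%, 87%, 82% and 77% adjusted. The absolute figures move, and adjustment still helps.

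**Step 5: attrition.** Section 5 expects that "approximately 67 will want additional treatment", which is about 75% of 90. As an illustration, let 25% leave after each of months 1, 2 and 3, missing at random, under the model of step 3. The ratio of adjusted to unadjusted standard error for r = 0.3, 0.5 and 0.7 is:

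- month 3: 0.975, 0.921, 0.806 (2%, 8% and 19% lower);
- month 6: 0.987, 0.955, 0.878 (1%, 4% and 12% lower).

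Starting from 45 per group, the month 6 half-width (1.96 × SE) goes from 10.0 to 9.9, from 9.1 to 8.6, and from 7.9 to 6.9.

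**Step 6: direction of the error.** In simulation at a true loss of 7.5 (stratified blocks, 90 analysed, two-sided 95% interval), the unadjusted analysis wrongly concluded non-inferiority in 2.5%, 2.3%, 2.1%, 1.7% and 1.0% of trials for r = 0.1, 0.2, 0.3, 0.5 and 0.7. The adjusted analysis did so in 2.4% to 2.5%. Omitting the covariates is conservative.

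**The case against.** The best case for the plan is that nothing in it is invalid. An unadjusted comparison by visit is unbiased, its error rate is at or below nominal, and the stated 80% power never depended on a covariate. On that view this is advice on efficiency, and its size cannot be established without r: at r of 0.3 or less, the gain at one-sided 5% is about 3 power points at most. The complete-data figures also flatter adjustment. Under the heavy attrition of step 5, the month 6 half-width stays above 7.5 at r = 0.3 and 0.5 with or without the covariate, so attrition and not the missing covariate would dominate. Finally, section 4 carries the last score forward, and under that rule the missing-at-random figures do not apply.

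Most of this is right, and it limits the point. It explains why this is a recommended improvement and not an error that threatens validity. It does not remove the point. The gain is never negative over the range examined, and at month 3, also a primary timepoint, it remains 8% of the standard error at r = 0.5 even in the heavy-attrition illustration. That illustration is itself severe, because section 3 allows patients to move on at any time up to 12 months. Carrying scores forward supplies no baseline adjustment. The model is the SAP's own content, so the omission is not something left to the protocol.

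**Conclusion.** The point holds, as a loss of precision and not as bias. Sub-study 1's model omits the baseline score and both stratification factors although the data for them exist, so the non-inferiority interval may be wider than necessary.

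The size is unknown because the SAP states no r. It is trivial at r of 0.2 or less, worthwhile from about 0.4, and large at 0.7, and it is smaller the more patients leave before the primary visits. These figures assume a true difference of zero and, outside step 5, complete data. They cover baseline VISA-A only; the further gain from symptom duration cannot be computed from the document. The sample size of 38 is not wrong for this reason, and the two-sided 95% power of 70% reflects the separate alpha mismatch.

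**What to change.** In SAP sections 5 and 7.2, for sub-study 1:

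- name continuous baseline VISA-A and the symptom-duration stratum as covariates;
- define the response as the post-baseline visits only, so that baseline is not also a level of time;
- include group-by-visit terms and read the month 3 and month 6 differences, with their intervals, from that model;
- confirm that the chosen software can fit this model.

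A lesser point, on precision only: the HVI-versus-CS comparison in sub-study 2 could be adjusted for VISA-A at entry to that sub-study. The stratification argument does not apply there, since "No further stratification will be carried out in part 2 of the study".

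The cost is a few lines of text and possibly another statistics package, with no new data and no extra patients. Section 7.4 says that no analysis had begun when the SAP was signed. The change should be dated before unblinding.
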